5.6.5 Reporting of Serious Adverse Events (SAEs)

In the case of a serious adverse event (SAE), the investigator must contact the sponsor immediately (within 24 hours of their knowledge of the event or at the earliest possible time point).

Information regarding serious adverse events will be transmitted to the sponsor using the Serious Adverse Event Form, which must be signed by investigator. The initial report of a serious adverse event may be made by email. It is preferable that serious adverse events be reported via email. A report of a serious adverse event must be followed by a completed Serious Adverse Event Form from the investigator.

In addition, the suspected unexpected serious adverse reactions (SUSAR) should also forward to IRB and health authority by the sponsor within the time frame according to the regulation of the health authority.

5.6.6 Follow-up to Adverse Events

All adverse events occurring during the study are to be followed up until resolved or judged to be no longer clinically significant, or until they become chronic to the extent that they can be fully characterized (all follow-up results are to be reported to the sponsor).

Since it is unpredictable how long such a follow-up will take, data from this follow-up generated after the subject's post study visit will be recorded by the investigator. Full details regarding this follow-up will be described in the study report, whenever necessary.

If during adverse event follow-up, the adverse event progresses to an "SAE", or if a subject experiences a new SAE whose relationship to the study drug(s) cannot be ruled out, the investigator must immediately report the information to the sponsor.

Even if the subject does not return to normal or to his or her previous state, the follow-up can be considered finished when the following procedures have been taken:

- The investigator judges that the follow-up of the subject concerned is no longer necessary based on the progress made during the follow-up,
- The reason for such a judgment is entered as a comment on the case report form for the follow-up, and
- The sponsor judges that the reason is acceptable with regard to the safety of the subject concerned.

5.6.7 Procedure in Case of Pregnancy

If it is subsequently discovered that a subject is pregnant during the study period, study treatment will be permanently discontinued in an appropriate manner. The Investigator must notify sponsor or its designee of this event within 24 hours of awareness. The pregnancy events require immediate notification to sponsor or its designee starting from the date of randomization until the last follow up visit. For the subject who withdraws the study during the treatment period, the pregnancy events should be reported to sponsor until 28 days after the last administration of study treatment. In addition, the Investigator must report to sponsor or its designee follow-up information regarding the course of the pregnancy, including perinatal and neonatal outcome.

5.6.8 Supply of New Information Affecting the Conduct of the Study

When new information necessary for conducting the clinical study properly is obtained, the sponsor should inform all investigators involved in the clinical study, IRB/IEC, as well as the regulatory authorities of such information, and when needed, should amend the subject information, written informed consent form and/or protocol on the matters covering the quality of the study drug, efficacy and safety, information necessary for conducting the clinical study properly, or documents to be examined by the IRB should be sent to the IRB.

5.6.9 Deviations from the Protocol and Other Actions Taken to Avoid Life-Threatening Risks to Subjects

The investigator must not deviate from or amend the protocol, excluding an emergency case for avoiding risks to the subjects. When the investigator does not follow the protocol in order to avoid urgent risks for subjects, the investigator should take the following actions.

- Describe the contents of the deviation or amendment and the reasons for it in a written notice, and immediately send the document stating the deviation or amendment and the reasons to the sponsor and the head of the study site. Keep a copy of the notice.
- Consult with the sponsor at the earliest possibility for cases in which it is necessary to amend the protocol. Obtain approval for a draft of the amended protocol from the IRB and the head of the study site as well as written approval from the sponsor.

6 TERMINATION OF THE CLINICAL STUDY

- When the sponsor is aware of information on matters concerning the quality, efficacy, and safety of the study drugs, as well as other important information that may affect proper conduct of the clinical study, the sponsor may discontinue the clinical study and send a written notice of the discontinuation along with the reasons to the investigator.
- If an investigator intends to discontinue participation in the study, the investigator must immediately inform the sponsor of the discontinuation and the reason for it.

7 STATISTICAL METHODOLOGY

7.1 Sample Size

The recent phase 2 clinical trial was carried out 30 subjects with Wagner-grade-1 chronic diabetic foot ulcers treated with ON101 for up to 12 weeks. The results showed that the incidence of healing by 12 weeks was 50% and the time of 50% subjects reached healing was approximately 10 weeks. Of the 30 subjects, treatment with ON101 for up to 12 weeks resulted in approximately 70% reduction of wound size. The average wound size at baseline was 577 mm² (303 - 1225 mm²), and decrease to 163 mm² for up to 12 weeks of ON101.

Sample size calculation is performed by the superiority test based on the incidence of complete healing of the target ulcer between the two treatment groups within 16 weeks. The ON101 cream will be considered to be effective if the complete healing rate is superior to the corresponding endpoint of the Aquacel[®] Hydrofiber[®] dressing at two-sided 5% significance level. The hypothesized complete healing rate difference between two treatment groups is 20%, assuming the rates are 50% for ON101 cream and 30% for Aquacel[®] Hydrofiber[®] dressing. This study is also planned two interim and 1 final analysis at around 50%, 90%, and 100% of study information, and the futility/superiority of ON101 cream will be assessed using the Lan-DeMets alpha-spending approach with an O'Brien-Fleming boundary.

Under the assumption described above and with a 1:1 randomization ratio of the two groups, a minimal 212 evaluable subjects will be required to achieve at least 80% power to detect a significant difference in complete healing rate using a 2-sided alternative at the 5% nominal significance level. Assuming the non-evaluability rate is 10%, a total of 236 subjects (118 subjects for ON101 cream and 118 subjects for Aquacel[®] Hydrofiber[®] dressing) will be enrolled into this trial.

7.2 Analysis Sets

In accordance with ICH recommendations in guidelines E3 and E9, the following analysis sets will be used for the analyses. Detailed statistical analysis information will be provided separately in the Statistical Analysis Plan (SAP).

7.2.1 Full Analysis Set (FAS)

The intent-to-treat (ITT) principal will be applied on the “full analysis set (FAS)”. The FAS includes all subjects who are randomized, irrespective of actual receipt of study intervention. This set will be the primary analyses population for all efficacy data. Under the ITT principle, all participants once randomized are analyzed according to the condition to which they were originally assigned, regardless of adherence with the protocol or the occurrence of adverse events. Thus, using the ITT principle, participants who were randomly assigned to the ON101 cream group but who received partial or none of the ON101 cream, would still be followed and analyzed

as if the participant received the ON101 cream. Participants randomly assigned to the Aquacel® Hydrofiber® dressing group but who received the ON101 cream would be retained in the Aquacel® Hydrofiber® dressing group and analyzed as if they received only the Aquacel® Hydrofiber® dressing.

7.2.2 Safety Analysis Set (SAF)

The “safety analysis set (SAF)” will include all randomized patients who received study intervention to the selected treatment area. This set will be used for the analyses of safety data. Safety will be assessed according to the treatment subjects actually received at least one dose of ON101 cream or Aquacel® Hydrofiber® dressing.

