5.1.3 Comparative Period

(Visit 3-Visit 10: Day 15 to Day 113)

The following procedures will be performed in this period:

- Apply test medication or comparative intervention

If complete wound healing by the judgment of independent reviewer happens before Visit 10, the applied test medication (ON101 cream) or comparative intervention (Aquacel® Hydrofiber® dressing) will be stopped at next scheduled visit which will be deemed as V10.

If the wound is unhealed at Visit 10, only Aquacel® Hydrofiber® dressing will be applied.

- Perform physical examinations and obtain vital signs
- Perform laboratory tests including hematology and biochemistry at Visit 4, Visit 6, Visit 8, Visit 10 and at the visit of early permanent discontinuation of study treatment
- 12 Lead ECG examination will be performed at Visit 10 or at the visit of prematurely discontinuation of study treatment
- Perform assessment of foot ulcer status and photography
- Standard ulcer care
- Perform assessment of adverse events
- Record concomitant medication

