5.1.4 Follow-up Period

(Visit 11-Visit 14: Day 127 to Day 197)

The following procedures will be performed in this period:

- Apply Aquacel® Hydrofiber® dressing to the subjects whose wounds are unhealed or recurrent
- Perform physical examinations and obtain vital signs

- Laboratory tests including hematology and biochemistry will be performed at Visit 14 (Week 28) or Visit of early permanent discontinuation during the follow-up period
- 12 Lead ECG examination will be performed at visit 14 (Week 28) or visit of early permanent discontinuation during the follow-up period
- Perform assessment of foot ulcer status and photography
- Standard ulcer care
- Perform assessment of adverse events
- Record concomitant medication

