5.5.2 Adverse Events

Adverse event collection will begin after study intervention initiated and continue through the entire study visit. All observed or spontaneously reported AEs will be recorded in the source documents and CRFs. Data to be recorded includes a description of the event, date of onset and end of the event, severity, action with respect to study intervention, treatment required, relationship to study intervention, and outcome of the event.

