7.5 Analysis of Safety

Adverse events will be regarded as Treatment Emergent (TEAE) if they started on or after the date and time of administration of the first dose of study intervention or if they were present prior to the administration of the first dose of study intervention and increased in severity during the study.

Adverse Events (AEs) will be coded using the standard Medical Dictionary for Regulatory Activities (MedDRA) dictionary and grouped by system organ class and preferred term and events. TEAEs will be summarized by frequency and proportion of total subjects, by system organ class and preferred terms. If appropriate, the incidence of adverse events (preferred terms and system organ class) will be compared for each of the two treatment groups using Fisher's exact test.

For the clinical laboratory and vital signs data, the data will be tabulated by treatment group for raw data and for change from baseline to evaluated time points; descriptive statistics to be provided include: n, mean, median, standard deviation, minimum and maximum. The differences between groups will be analyzed by analysis of covariance (ANCOVA) with factor being fitted for treatment, and baseline value fitted as a covariate. Subjects with laboratory data outside the normal range will be listed and abnormal values will be flagged.

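### Adverse-event incidence is counted past the end of ON101 treatment, and the safety set does not say where ON101 subjects who later receive Aquacel belong

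*Combined protocol and SAP*

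**What the plan says.** **Grouping.** Section 7.2.2 reads "Safety will be assessed according to the treatment subjects actually received at least one dose of ON101 cream or" Aquacel. It gives no rule for a subject who has had both. For efficacy, section 7.2.1 settles crossover by original assignment; 7.2.2 has no equivalent.

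**Window.** Under section 7.5 an event is treatment-emergent "if they started on or after the date and time of administration of the first dose of study intervention", or if it was already present and "increased in severity during the study". Neither clause has an end date. Section 5.5.2 states: "Adverse event collection will begin after study intervention initiated and continue through the entire study visit".

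**Comparison.** Section 7.5 says that, if appropriate, "the incidence of adverse events (preferred terms and system organ class) will be compared for each of the two treatment groups", by Fisher's exact test.

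**Change of treatment.** ON101 is applied for at most 16 weeks (section 5.2.1). After early healing, the assigned product "will be stopped at next scheduled visit which will be deemed as V10" (section 5.1.3). A wound still open at Visit 10 receives Aquacel only. In follow-up, Aquacel goes as a "dressing to the subjects whose wounds are unhealed or recurrent" (section 5.1.4). Section 2.2.1 follows every subject for 12 more weeks.

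**The concern.** Read together, these sections put two different periods into one incidence figure: time on the randomized product, and up to 12 weeks in which no subject is on ON101. Healed subjects in both arms use neither product in follow-up unless the wound recurs. Unhealed and recurrent subjects in both arms use Aquacel. If ON101 raises the risk of some event only while it is applied, the second period adds similar background events to both arms and pulls their ratio toward 1.

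The grouping gap is separate. An ON101 subject who moves to Aquacel at Visit 10 satisfies the wording of 7.2.2 for both products. This is a planned part of the design, not a rare misallocation.

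Safety information is a stated objective (section 2.1), and section 10.1 allows early stopping for unacceptable toxicity. The window and the groups should be fixed before unblinded tables exist, because the choice changes those tables.

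**Working it through.** The documents give no event rates and no safety sample size, so there is no safety figure to reproduce. The arm size follows from section 7.1: 212 / 0.90 = 235.6, hence 236, or 118 per arm.

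**1. Share of the schedule off ON101.** Visit 10 is Day 113 and Visit 14 is Day 197. (197 − 113) / (197 − 1) = 84 / 196 = 43%, or 12 of 28 weeks.

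**2. Subjects exposed to both products.** With the 50% healing rate of section 7.1, 118 × (1 − 0.50) = 59 ON101 subjects, plus recurrences and less any who leave before follow-up.

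**3. Effect confined to time on drug.** Assumptions:
- 16-week risks of 20% (ON101) and 10% (Aquacel), with constant hazards.
- Healing in 50% and 30% of subjects (section 7.1); healers reach Visit 10 at Week 10 and all others at Week 16.
- 12 weeks of follow-up at the Aquacel-arm hazard in both arms, with no dropout.

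Weekly hazards are −ln(0.80)/16 = 0.01395 and −ln(0.90)/16 = 0.00659.

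On treatment:
- ON101: 0.5 × (1 − e^(−0.1395)) + 0.5 × 0.20 = 0.5 × 0.1302 + 0.10 = 16.5%.
- Aquacel: 0.3 × (1 − e^(−0.0659)) + 0.7 × 0.10 = 0.3 × 0.0637 + 0.07 = 8.9%.

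Whole study, with 12-week event-free factor e^(−0.0790) = 0.924:
- ON101: 1 − 0.8349 × 0.924 = 22.9%.
- Aquacel: 1 − 0.9109 × 0.924 = 15.8%.

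Exact power of Fisher's test uses 118 per arm and two-sided 0.05. Each cell shows on treatment → whole study.

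| 16-week risks | Healers' Visit 10 | Risk ratio | Risk difference (points) | Power |
|---|---|---|---|---|
| 20% vs 10% | Week 10 | 1.85 → 1.44 | 7.6 → 7.0 | 34% → 23% |
| 20% vs 10% | Week 6 | 1.72 → 1.36 | 5.9 → 5.4 | 23% → 15% |
| 20% vs 10% | Week 14 | 1.96 → 1.52 | 9.2 → 8.5 | 46% → 31% |
| 15% vs 5% | Week 10 | 2.77 → 1.94 | 7.9 → 7.6 | 50% → 36% |

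Power falls although the difference barely moves, because the added background events raise the variance in both arms.

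**4. Simpler model.** Everyone is treated for 16 weeks, with an on-drug hazard ratio of 2. At 5%, 10% and 20% background 16-week risk, the ratio goes 1.95 → 1.53, 1.90 → 1.49 and 1.80 → 1.42. The difference goes 4.8 → 4.6, 9.0 → 8.3 and 16.0 → 13.5 points. Power goes 20% → 15%, 43% → 30% and 75% → 53%.

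**5. Effect that persists after stopping.** At 10% background and a hazard ratio of 2 throughout, the 28-week risks are 1 − 0.9^3.5 = 30.8% and 1 − 0.9^1.75 = 16.8%. The difference rises from 9.0 to 14.0 points and power from 43% to 67%. Here whole-study counting is the better detector.

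**6. Length of observation.** Mean comparative-period time is 0.5 × 10 + 0.5 × 16 = 13.0 weeks on ON101 and 0.3 × 10 + 0.7 × 16 = 14.2 weeks on Aquacel, or 8.5% less. For healers at Week 14 to Week 6 the gap is 2.6% to 15%. If the 12 weeks run from the deemed Visit 10, totals are 25.0 and 26.2 weeks, or 4.6% less. If follow-up keeps its fixed days, totals are equal.

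**The case against.** - **The grouping rule has an ordinary reading.** The schedule's footnote makes Visit 10 the end of study treatment, so the product received is naturally the one given up to then. This largely stands. A reader might infer that switchers would be counted under Aquacel; in the simpler model that would take the ratio down to about 1.24–1.31 at a hazard ratio of 2. Nothing in the documents says this would be done. The fault is that the rule is not stated.
- **The dilution is mostly on the ratio scale and is conditional.** This stands. The absolute excess moves by 0.3 to 0.7 points in the table above, and the loss depends on the effect ending with treatment, which the documents neither assert nor exclude.
- **The errors need not favour ON101.** A reader might infer that the plan is tilted toward the test product. If ON101 causes fewer events, dilution works against it. Shorter observation of the faster-healing arm over the whole study depends on how follow-up is timed, and early exits for worsening to Wagner grade 3 could shrink or reverse the gap.
- **Safety is not powered.** Section 7.5 makes the Fisher test conditional, and the synopsis promises only a numerical comparison. The power figures therefore illustrate lost information, not a failed design requirement.
- **A separate SAP may hold the cut.** Section 7.2 defers detail to one, and its text is not in the material reviewed. But section 7.5 itself defines the window, so the limit belongs there too.
- **Laboratory and vital signs.** Section 7.5 analyses these by time point, so Week 28 is already separate. The point is confined to adverse-event incidence.

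**Conclusion.** The point holds for adverse-event incidence. As written, the between-group count runs past the end of ON101 treatment for 12 of 28 scheduled weeks, and about 59 of 118 ON101 subjects have no stated safety group. For an effect confined to time on drug, the risk ratio falls from about 1.85 to 1.44 (from 1.72–1.96 to 1.36–1.52 as healers' Visit 10 varies from Week 6 to Week 14), while the risk difference changes little. These sizes rest on assumed event risks, constant hazards, the planned healing rates and no dropout. The documents do not support saying that a safety signal would be concealed in general, or that the plan is biased toward ON101. This is a worthwhile and inexpensive improvement: neither window alone serves every kind of effect, so both should be shown.

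**What to change.** - **Section 7.2.2:** assign the safety group by the treatment received in the comparative period, and say that Aquacel given in follow-up does not change it.
- **Section 7.5:** report and compare treatment-emergent events with onset from first dose to Visit 10, using the deemed Visit 10 for early healers.
- **Follow-up:** tabulate these events separately, by the same group and by whether Aquacel was applied.
- **Whole study:** keep this table alongside, so that delayed or persistent events remain visible.
- **Exposure:** add exposure-adjusted incidence rates next to the crude percentages. The period to Visit 10 varies with healing and early exit, so limiting the window without this adjustment would carry the 8.5% gap in step 6.

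Repeat the wording in the SAP. Section 5.5.2 already records onset dates, and section 8.1.2 lists visit dates among source data. A window ending at Visit 10 is safer than one ending at last application, because the documents do not say that the last application date is captured. Confirm that the CRF records Aquacel use at follow-up visits.

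The cost is a few extra tables and fewer events in each period table. Trial conduct does not change.

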7.2.3 Supportive Analysis Population

Subjects in FAS with eligible target ulcer at baseline will be included as modified ITT (mITT) population. mITT will be used for supportive analyses of efficacy data as appropriate.

7.3 Demographics and Other Baseline Characteristics

The demographics and baseline wound characteristics (ulcer severity, etiology, location and size) of subjects will be collected at screening period or Day 1 (before study intervention applied). These variables will be summarized by descriptive statistics for two treatment groups. For continuous variables, the number, mean, standard deviation, median, minimum, and maximum values will be presented. Besides, an analysis of variance (ANOVA) test will also be performed for continuous variables to test the comparability for two randomized groups.

For categorical variables, the numbers and percentages of subjects in each class will be listed, and the Fisher’s exact test for two treatment group comparison will also be performed.

7.4 Analysis of Efficacy

7.4.1 Analysis of Primary Variable

The primary efficacy variable is the proportion of subjects whose target ulcer is complete healing. The definition of complete healing for the target ulcer is complete epithelialization which is maintained with no drainage for at least 2 weeks and is confirmed by a blinded independent evaluator.

This will be a multi-center study. It is anticipated that the number of participating centers can be large and the number of subjects enrolled at each center could be small. As a result, the data from all centers will be pooled for statistical analyses.

The hypothesis for the comparison is given as follows:

H_0 : The healing rates on ON101 cream and Aquacel® Hydrofiber® dressing are the same

H_1 : The healing rates on ON101 cream and Aquacel® Hydrofiber® dressing are not the same

The number of percentage of subjects achieving the efficacy endpoints will be summarized by visit and ON101 cream group will be compared to the Aquacel[®] Hydrofiber[®] dressing group with Chi-square test. The logistic regression model with treatment/intervention as fixed factor, and baseline wound size and Wagner grade as covariates will be applied to the primary analysis of primary endpoint. The results of the logistic regression model will be presented in terms of the odd ratio (ON101 cream versus Aquacel[®] Hydrofiber[®] dressing), with p-values and associated 95% confidence intervals of the odds ratio.

The test intervention (ON101 cream) will be concluded to be superior to the control (Aquacel[®] Hydrofiber[®] dressing) in average if the null hypothesis (H_0) is rejected and the odds ratio higher than 1. To reflect the interim analysis, final analyses will be based on a Type I error rate (two-sided) of 0.039611.

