7.6.2 Interim Analysis

Two Interim Analyses will be conducted when 118, and 212 subjects complete the comparison period or early withdraw from study intervention on a sequential basis. This will be about 50% and 90% of the total number of subjects that will be randomized.

The independent Data Monitoring Committee (IDMC) will review the results of the interim analyses for a possible early termination of the trial due to an overwhelming efficacy results based on pre-defined alpha specified based on O'Brien-Fleming alpha-spending function specified in this protocol and detailed in the Statistical Analysis Plan(SAP). The statutes of the IDMC will be defined in advance and will be included in a separate charter.

The Lan and DeMets version (Lan and DeMets, 1983) of the O'Brien-Fleming alpha-spending function is used to calculate the Type I Error rate alpha, to maintain the trial-wise 5% type I error. Because the 1st interim analysis has been conducted at 124 subjects who complete the comparison period, the alpha boundary will be estimated based on 53% information for the 1st interim analysis. The proportion of the overall number of target subjects (a total of 236 subjects) included in the analyses at each point and alpha boundaries used to assess significance at each analysis are as follows.

Analysis number	% of randomized subjects	Alpha Boundary
1. Interim Analysis 1	53%	0.003957
2. Interim Analysis 2	90%	0.034760
3. Final	100%	0.039611

As the 1st IA failed to meet the boundary of (0.003957); a 2nd IA will be conducted. Based on the above mentioned boundary for the 2nd IA, the IDMC can stop the trial if the observed p-value is less than 0.034760, the alpha presented above.

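### The primary odds ratio carries a 95% interval while the final test uses 0.039611, so the interval can exclude 1 at the final analysis without superiority being shown (minor; the decision rule itself is sound)

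*Combined protocol and SAP*

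**What the plan says.** Section 7.4.1 makes a logistic regression the primary analysis, with treatment as factor and "baseline wound size and Wagner grade as covariates will be applied to the primary analysis of primary endpoint". Results are given as the odds ratio of ON101 to Aquacel "with p-values and associated 95% confidence intervals of the odds ratio". The Statistical Methods entry of the Synopsis also specifies 95%.

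The next paragraph of 7.4.1 concludes superiority "if the null hypothesis (H_0) is rejected and the odds ratio higher than 1" and sets the level: "final analyses will be based on a Type I error rate (two-sided) of 0.039611".

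Section 7.6.2 explains that level. Lan-DeMets spending of O'Brien-Fleming type is used "to maintain the trial-wise 5% type I error", with nominal two-sided boundaries of 0.003957, 0.034760 and 0.039611. The first look has taken place and missed its boundary. At the second, "the IDMC can stop the trial if the observed p-value is less than 0.034760".

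The text supplied does not define an interval at an adjusted level or a repeated confidence interval, and does not say that the 95% interval is descriptive. Sections 7.2 and 7.6.2 refer to a separate SAP for detail; its text is not included.

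**The concern.** A 95% interval corresponds to a two-sided test at 0.05, and 0.05 is not the threshold at any of the three looks. Section 7.4.1 lowers the test level because of the interim analyses but leaves the interval at its fixed-sample level, although the same reason applies to both.

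What is at stake is the reported estimate of the primary effect. Many readers judge superiority by whether the interval for the odds ratio excludes 1. At the final analysis that habit can produce a claim that the plan's own rule denies, with both statements drawn from the same model.

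**Working it through.** **Inputs.** Boundaries 0.003957, 0.034760 and 0.039611 (7.6.2; the last also in 7.4.1). First look at 124 subjects ("the 1st interim analysis has been conducted at 124 subjects who complete the comparison period"), second planned at 212, total 236 (7.6.2). Rates 50% and 30%, 118 per arm (7.1). The rates of 40% and 45% for ON101 are my assumptions, added to show a smaller effect.

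**1. The plan's boundaries reproduce.** I spent 0.025 per side with the O'Brien-Fleming-type function.
- At information 124/236 = 0.5254, 212/236 = 0.8983 and 1, the nominal levels are 0.003974, 0.034791 and 0.039600.
- At 0.525, 0.898 and 1 they are 0.003957, 0.034757 and 0.039611.
- The stated boundaries give an overall two-sided error of 0.04998.

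The test is therefore sound. Only the interval is in question.

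**2. Interval that matches each test.** Level = 1 − alpha; relative width on the log-odds scale = z(1 − alpha/2) / 1.9600.

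| Look | Alpha | z | Matching level | Width relative to 95% |
|---|---|---|---|---|
| Second interim | 0.034760 | 2.1111 | 96.52% | 1.077 |
| Final | 0.039611 | 2.0578 | 96.04% | 1.050 |

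**3. Where interval and test disagree.** At the final analysis they disagree when |z| lies between 1.960 and 2.058, that is, p between 0.039611 and 0.05. At the second interim, stopping for efficacy needs |z| above 2.111, which already exceeds 1.960, so the 95% interval also excludes 1.

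**4. An example at the final analysis** (unadjusted Wald, 118 per arm, 50 against 35 healed).
- Log odds ratio = ln[(50/68)/(35/83)] = 0.556, so the odds ratio is 1.744.
- Standard error = √(1/50 + 1/68 + 1/35 + 1/83) = 0.2745.
- z = 0.556/0.2745 = 2.026, p = 0.0428.
- 95% interval: exp(0.556 ± 1.960 × 0.2745) = 1.018 to 2.986, which excludes 1.
- 96.04% interval: exp(0.556 ± 2.058 × 0.2745) = 0.991 to 3.067, which includes 1.

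Since 0.0428 is above 0.039611, superiority is not shown. Only the second interval agrees with that.

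**5. How often.** I simulated three-look trials under a normal approximation, with the stated boundaries and mean final z = (p1 − p2)/√{[p1(1 − p1) + p2(1 − p2)]/118}. At 50% against 30% this is 0.20/√(0.46/118) = 3.203.

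| ON101 vs Aquacel | Final reached, 95% interval excludes 1, no rejection | Same, among trials reaching the final |
|---|---|---|
| 30% vs 30% | 0.8% (0.4% favouring ON101) | 0.8% |
| 40% vs 30% | about 2.6% | 3.7% |
| 45% vs 30% | about 2.6% | 6.1% |
| 50% vs 30% | 1.4% | 8.0% |

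The middle column counts from the start of the trial. Given that the first boundary was missed, the design-rate figure is divided by the chance of missing it: Φ(2.8816 − 3.203 × √0.5254) = Φ(0.560) = 0.712, and 1.4%/0.712 is about 2.0%.

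**6. Coverage.** The unadjusted 95% interval, taken at whichever look the trial stops, covers the true effect about 94.3% of the time under no difference and just under 94% at 40% against 30%. The boundary-matched interval covers at least 95%.

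**The case against.** The strongest reply is that the interval decides nothing. Section 7.4.1 ties superiority to rejecting the null hypothesis with an odds ratio above 1, 7.6.2 ties stopping to the p-value, and the adjusted alpha stands in the same section as the interval. An interval labelled 95% is a conventional summary and is not presented as the test. All of that stands. It protects the decision but not the reported estimate, whose coverage falls below its label and which carries no caution.

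A reader might infer four stronger things that the documents do not support:
- **That the trial's type I error is inflated.** Reading the final result from the 95% interval would raise it from 0.050 to about 0.0575, but the plan does not judge superiority that way.
- **That the contradiction also arises at the second interim.** Step 3 rules this out after an efficacy stop. If the trial continues, 7.6.1 and 10.1 bar the IDMC from disclosing results beyond its recommendation to continue.
- **That 0.8% is the risk of a false superiority reading.** That figure counts both directions; the part favouring ON101 is 0.4%.
- **That 8.0% is the risk at the design rates.** It applies only to trials that reach the final analysis, about 18% of them (1.4%/8.0%).

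The separate SAP may already define an adjusted interval. Section 7.4.1 and the Synopsis would still specify 95%.

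**Conclusion.** The point holds as a minor inconsistency in reporting the primary endpoint. The test, its boundaries and the superiority rule are sound. The 95% interval is too narrow for the test it accompanies: the matching interval is 5.0% wider at the final analysis and 7.7% wider after a stop at the second interim. An actual contradiction is confined to a final p between 0.0396 and 0.05. Its chance is below 3% in every scenario examined.

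The frequencies assume 118 analysed per arm, looks at 124, 212 and 236 subjects, and a normal approximation without covariates. Adjusting for wound size and Wagner grade would change the figures. It would not change the link between p-value and interval, provided both come from the same method (for example Wald).

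**What to change.** In 7.4.1 and the Synopsis, replace the 95% interval for the primary odds ratio with the boundary-matched (repeated) confidence interval: 96.04% (1 − 0.039611) at the final analysis, or 96.52% (1 − 0.034760) if the trial stops at the second interim. State that the interval and the p-value come from the same method. If a 95% interval is shown as well, label it nominal, unadjusted for the interim looks and not for judging superiority. Carry the same wording into the separate SAP if it does not already have it.

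The cost is one sentence in each place and an interval about 5% to 8% wider. Sample size, alpha allocation and trial conduct are unaffected.
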